19.3 Definitions of serious adverse events including serious health threat and serious adverse device effects and, where appropriate, unanticipated serious adverse device effects.

The terms and definitions presented below are covered by the ISO standard 14155:2020 "Clinical investigation for medical devices for human subjects: good clinical practice"

Investigational	Medical device being assessed for safety or performance in a clinical investigation.
medical device	This includes medical devices already on the market that are being evaluated for new intended uses, new populations, new materials or design changes.
Adverse Event (AE)	Any untoward medical occurrence, unintended disease or injury or any untoward clinical signs (including an abnormal laboratory finding) in subjects, users or other persons whether or not related to the investigational medical device.
	This definition includes events related to:
	 the investigational device or the comparator. the procedures involved.
	For users or other persons, this definition is restricted to events related to investigational medical devices.
Serious	Adverse event that:
Adverse Event (SAE)	a) led to a death, injury or permanent impairment to a body structure or a body function.
(OAL)	b) led to a serious deterioration in health of the subject, that either resulted in:
	- a life-threatening illness or injury, or
	- a permanent impairment of a body structure or a body function, or
	- in-patient hospitalization or prolongation of existing hospitalization, or
	- in medical or surgical intervention to prevent life threatening illness
	c) led to foetal distress, foetal death or a congenital abnormality or birth defect.
	Planned hospitalization for pre-existing condition, or a procedure required by the Clinical Investigation Plan, without a serious deterioration in health, is not considered a serious adverse event.
Adverse Device	Adverse event related to the use of an investigational medical device.
Effect (ADE)	NOTE 1- This includes any adverse event resulting from insufficiencies or inadequacies in the instructions for use, the deployment, the implantation, the installation, the operation, or any malfunction of the investigational medical device.
	NOTE 2- This includes any event that is a result of a use error or intentional abnormal use of the investigational medical device.

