Serious Adverse Device Effect (SADE)	Adverse device effect that has resulted in any of the consequences characteristic of a serious adverse event.
Device deficiency	Inadequacy of an investigational medical device related to its identity, quality, durability, reliability, safety or performance. This may include malfunctions, use error, or inadequacy in the information supplied by the manufacturer.
Unanticipated Serious	Serious adverse device effect which by its nature, incidence, severity or outcome has not been identified in the current version of the risk analysis report.
Adverse Device Effect (USADE)	NOTE: Anticipated SADE (ASADE): an effect which by its nature, incidence, severity or outcome has been previously identified in the risk analysis report

19.4 List of non-reportable adverse events, if applicable, including rationale.

Not applicable

19.5 Time period in which the principal investigator shall report all adverse events and device deficiencies to the sponsor and, where appropriate, to ECs and the regulatory authority.

Upon being made aware of a SADE/USADE, the CI will notify the Sponsor ([contact]) and the CRO (www.pharmexcel-cro.com) within 24 hours, with subsequent notification of the MHRA and REC within 15 days of completion of the SADE report.

19.6 Details of the process for reporting adverse events.

Any adverse event reported by participants or observed by the investigators involved in the study will be screened by the Research Team in the first instance. If the report is deemed an adverse event (e.g. user error), it will be recorded using an adverse events form which will be sent to the Monitor (PHARMExcel) who will adjudicate and USADEs will be reported to the MHRA and the sponsor. All staff will be GCP trained. A data monitoring committee will provide overall oversight.

When an unacceptable risk to participants' health and safety is identified the medical device will be recalled following the below procedure:

- 1. Participant communication: If a device fault poses an unacceptable risk, participants will receive communication explaining the recall reason. They will also be provided with a contact person (usually the project PI or clinical lead) to address any concerns or discuss the matter.
- 2. Return process: Participants will receive a postal address to return the faulty device and postage costs will be reimbursed.

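### Section 19.6 gives user error as its example of an adverse event, whereas the section 19.3 definitions class a use error as a device deficiency unless an event results from it

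*Protocol*

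**What the plan says.** Section 19.6 of the protocol starts from reports that are already called adverse events: "Any adverse event reported by participants or observed by the investigators involved in the study will be screened". The research team does this first screening. The section then says: "If the report is deemed an adverse event (e.g. user error), it will be recorded using an adverse events form". User error is the only example given. Completed forms pass to the monitoring organisation for adjudication.

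Section 19.3 defines the classes:

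- Adverse event: "Any untoward medical occurrence, unintended disease or injury or any untoward clinical signs", whether or not related to the device.
- Adverse device effect: an adverse event related to use of the device. Note 2 adds: "This includes any event that is a result of a use error or intentional abnormal use of the investigational medical device".
- Device deficiency: an inadequacy of the device. "This may include malfunctions, use error, or inadequacy in the information supplied by the manufacturer".
- Serious adverse event, limb (a): an adverse event that "led to a death, injury or permanent impairment to a body structure or a body function". Limb (b): one that "led to a serious deterioration in health of the subject, that either resulted in" any of a list of outcomes, the first of which is an illness or injury that threatens life.

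Device deficiencies have their own reporting route in 19.7. Section 12.2 presents adverse events by treatment arm. Section 8.3 makes a list of adverse reactions a secondary outcome. Section 7.4 names ease of use and safety as separate parts of the home-use hypothesis, with absence of adverse events as the example of safety.

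**The concern.** The example in 19.6 names a cause (the user did something wrong) where 19.3 requires a consequence (something happened to the person's body). Two members of staff could take the same report, one working from 19.6 and the other from the 19.3 table, and put it in different classes.

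The situation is foreseeable. Participants fit the garment, apply gel and connect the colour-coded snaps themselves (4.1, 4.7), at home, on at least 5 days in 7 for 12 weeks (10.1). If a handling slip is recorded as an adverse event, a problem of ease of use enters the safety result. Section 7.4 keeps the two apart.

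The secondary point lies inside the serious adverse event definition. Injury in limb (a) carries no degree of severity, while limb (b) mentions injury only when it threatens life. If limb (a) is read at its widest, that item of limb (b) adds nothing. The class matters because a serious event that is device-related becomes a serious adverse device effect, which sets off the notification timelines in 19.5.

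**Working it through.** No sample size, power or event-rate calculation bears on this point, and the protocol states no expected count of adverse events, serious adverse events or use errors. There is therefore no figure to reproduce, and the check is a comparison of texts.

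**Step 1: three illustrative reports classified under each section.** The reports are illustrations, not taken from the protocol.

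| Report | Under the 19.3 definitions | Under the 19.6 example, read literally |
|---|---|---|
| A. Snaps paired wrongly, no symptom | Use error, so device deficiency; no medical occurrence, so no adverse event | Adverse event |
| B. Snaps paired wrongly, a skin reaction follows | Adverse event and, through Note 2, adverse device effect | Adverse event |
| C. Correct use, a skin reaction follows | Adverse event; adverse device effect if related to the device | Adverse event |

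The sections agree on B and C and part only on A. The conflict is therefore confined to use errors without a medical occurrence.

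**Step 2: do later steps remove the conflict?** Reports are screened before a form is completed, and forms are adjudicated afterwards. Either step could move report A out of the adverse-event class. However, 19.6 gives no criterion for either step, and the only illustration it offers points the wrong way. The outcome would depend on whether the person deciding follows the example or the table.

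**Step 3: where the class is used.** Sections 12.2 and 7.4 both rely on it. At the planned 40 participants per arm (12.5.6), one participant wrongly counted as having had an adverse event moves that arm's proportion by 1/40 = 2.5 percentage points. This shows only how sensitive the table is. How many participants would be affected cannot be derived from the protocol.

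**Step 4: the two limbs of the serious adverse event definition.** Limb (a) covers an event that led to an injury, with no severity attached. Limb (b) requires serious deterioration in health and, within that, an injury that threatens life. Any event that led to a life-threatening injury already satisfies limb (a), so that part of limb (b) is redundant on a literal reading. This is an overlap within one definition.

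**The case against.** The strongest reply is that 19.6 can be read consistently with 19.3. Its opening sentence concerns adverse events that have been reported or observed, so the parenthesis may mean an adverse event caused by user error, which is what Note 2 describes. Screening and adjudication also come before any count, and completing a form is not the same as entering a case in the analysis. This stands in part. A consistent reading exists and may well be what was intended, but the words name the error and not the event resulting from it.

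A reader might go further in four ways that the protocol does not support:

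- **That the safety counts by arm are wrong.** No counts exist, two review steps precede them, and the comparison is descriptive. Only a risk of inflation or inconsistency is shown.
- **That use errors would be lost from the deficiency record, or that differences in skin reactions would be diluted.** Section 19.7 keeps a separate deficiency route, and nothing makes the two records exclusive. Skin reaction is listed as its own data item (10.5), and usability has its own questions at week 12 (Table 1).
- **That treating any injury as serious goes against the protocol's definitions.** Limb (a) is the protocol's definition. Nor does it follow that every injury is serious: limb (a) concerns an event that led to an injury, which need not include an event that is itself an injury and has no further result. Section 19.8 calls skin irritation a foreseeable adverse event and treats serious irritation separately.
- **That a multiple can be put on the inflation.** Any such figure would only restate the use-error and adverse-event rates assumed for it.

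**Conclusion.** The conflict is real but narrow. The example in 19.6 disagrees with the adverse event and device deficiency definitions in 19.3 for one kind of report: a use error with no medical occurrence. Such reports could be recorded as adverse events, so the data by arm and the safety part of the home-use hypothesis could be inflated or classified inconsistently.

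The size cannot be stated, because no rates are given and the effect of screening and adjudication is unknown. The conclusion assumes only that some staff will take the example at face value.

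The injury wording is a secondary drafting point. Limbs (a) and (b) overlap and need to be reconciled, but nothing in the protocol shows that serious events would be miscounted.

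**What to change.** In 19.6, delete the parenthesis or reword it so that a report is an adverse event only if it meets the 19.3 definition; an event resulting from a use error would be a suitable example. Add that a use error without a medical occurrence is recorded as a device deficiency under 19.7. The layout of the safety tables can be left to the statistical analysis plan.

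In 19.3, the sponsor should reconcile limb (a) with limb (b), and both with the ISO standard that the section cites. Which events count as serious, and so which reporting route they follow, is for the sponsor to settle. This review does not choose the rule.

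The cost is a few words in a protocol amendment, approved as section 14 requires, and a briefing for the staff who screen reports and for the monitor. No additional participants or assessments are needed.
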